1. PRELIMINARY OVERVIEW

1.1 Study Synopsis

1.1.1 Administrative Information

Administrative Information					
Study Title A Prospective Single Center Clinical Study for Femtosecond Laser Glaucoma Surgery Using the ViaLase Laser					
Study Number	VIA-001				
Study Sponsor	ViaLase Inc. [name]				

1.1.2 Study Architecture

Study Architecture	
Study Design	This is a prospective, single-center, and single arm clinical trial of ViaLase Laser for the treatment of primary open angle glaucoma. Subjects will be screened for qualification as per the inclusion/exclusion criteria and must meet the inclusion/exclusion criteria in at least one eye to be enrolled. Up to 20 subjects will be consented as per the informed consent process. Subjects will be treated with the ViaLase Laser in one eye and followed for up to 12 months.
	Subjects will be screened for eligibility and informed consent will be obtained from consecutive subjects who meet screening criteria and are willing to participate in the study. Eligible subjects will be examined preoperatively to obtain a medical history and to establish a baseline ocular condition. Baseline and postoperative measurements will include distance visual acuity, manifest refraction, diurnal intraocular pressure, slit-lamp examination, gonioscopy, visual field, dilated fundus examination, specular microscopy, and pachymetry.
	Patient will continue use of IOP-lowering medications prior to surgery and up to 1 month post-operatively. The investigator has discretion to add, continue or remove medication thereafter.
	This study is being conducted in accordance with good clinical practice (GCP). Protocols have been submitted to and approved by an Ethics Committee for a study in patients freely providing informed consent. Data reporting, adverse event reporting and data collection is described in this protocol.
Study Location	Semmelweis University, Budapest, Hungary

1.1.3 Study Summary

Study Summary						
Study Objective	The purpose of study is to obtain initial evidence of the safety of image guided, femtosecond laser glaucoma surgery using the ViaLase Laser for the treatment of primary open angle glaucoma.					
Study Population	Subjects at least 45 years of age, of either sex, and any race or ethnicity, with refractory Primary Open Angle Glaucoma (POAG) with IOP between 21 and 35 mmHg using 1 or more IOP lowering medications.					
Safety Outcomes	Immediate safety outcomes will be assessed during the Operative day (day-0), 1-day and 1-week visits:					
	 Percentage patients with elevated IOP equal or greater than 6 mmHg at 1-hour post-treatment 					
	Percentage of patients with iritis, anterior chamber flare and cells					
	Percentage of patients with Hyphema					
	Percentage of patients with corneal haze					
	Additional, longer-termed, safety outcomes will be assessed by monitoring clinical data including:					
	 Changes in best spectacle corrected visual acuity (BSCVA) 					
	Peripheral anterior synechiae (PAS)					
	Cornea endothelial cell count					
	Endothelial cell count					
	Slit lamp findings					
	Corneal thickness (pachymetry)					
	Visual field					
	Fundus findings					
	Other gonioscopic findings additional to PAS					
	The number of glaucoma medications used					
	Adverse events					
	Procedure-related complications					

Study Summary						
Adverse Events	All adverse events will be summarized, tabulated, and analyzed by: Seriousness Severity Outcome Relationship to the study device Relationship to the study procedure.					
Examination Schedule	The examination schedule for study subjects will be as follows: Subject Eligibility Preoperative Evaluation Operative Evaluation Postoperative Day 1 Postoperative Week 1 Postoperative Month 1 Range 5 - 9 days post-op Postoperative Month 3 Range 70 – 105 days post-op Postoperative Month 6 Range 168 – 196 days post-op Postoperative Month 12 Range 330 – 420 days post-op					
Compliance	This clinical investigation will be conducted in accordance with the ethical principles that have their origin in the Declaration of Helsinki, ISO 14155:2011 (Clinical Investigation of Medical Devices for Human Subjects – Good Clinical Practice), ICH-GCP, and any regional or national regulations, as appropriate. This may include an inspection by ViaLase representatives and/or Regulatory Authority representatives at any time. The investigator agrees to allow the inspection of study-related records by the Regulatory Authority or ViaLase representatives. Regulatory Authority approvals, authorizations, and notifications, where required, will also be in place and fully documented prior to study start.					

1.2 Study Rationale

Glaucoma is a collection of disorders characterized by progressive loss of visual field due to optic nerve damage. It is the leading cause of global irreversible blindness effecting approximately 64.3 million people in 2013. Global estimates project the incidences of glaucoma will increase to 76.0 million in 2020 and 111.8 million people in 2040 (1). In the United States, nearly 3 million Americans have glaucoma, while another 10 million are at risk due to statistically significant elevation of the IOP (1; 2). Eyes with Primary Open-Angle Glaucoma (POAG) present elevated intra ocular pressure (IOP), though elevated IOP

is not a necessary indication for glaucomatous damage (3). It is generally bilateral, but often asymmetric. POAG is believed to be caused by an increased resistance to the normal outflow of aqueous humor from the eye. The major source of outflow obstruction that raises intraocular pressure (IOP) is thought to be the juxtacanalicular trabecular meshwork (TM), and an increase in the accumulation of extracellular material in both the TM and ciliary muscle, which further contribute to the reduction of normal outflow, resulting in increased IOP (4; 5; 6). Elevated IOP eventually leads to an acquired optic neuropathy in which the neuro retinal rim is thinned due to loss of retinal ganglion cells. When loss of optic nerve tissue is significant, patients develop optic nerve related visual field loss.

Management of glaucoma requires chronic, life-long treatment with a spectrum of therapeutic options including medications (7), laser treatment (8; 9; 10; 11), ab-interno trabeculectomy (12), and surgically implanted internal or external drainage devices (12; 13; 14; 15; 16). The common goal among the various therapies is to lower intraocular pressure (IOP) to target levels to prevent loss of visual fields from excessive pressure on the optic nerve. In order to relieve elevated IOP, it is proposed to increase the outflow through the juxtacanalicular trabecular meshwork by surgically creating canals that span from the anterior chamber, through the juxtacanalicular trabecular meshwork, and reaching the inner wall of Schlemm's canal. Such a canal can clear the outflow obstruction and provide a fluid pathway for aqueous humor.

One such therapy is the minimally invasive glaucoma surgery (MIGS) in which a trans-trabecular shunt is implanted. The interest in MIGS stems from a desire for an alternative surgical option for the treatment of glaucoma that is associated with less risk and fewer complications than established procedures. Furthermore, MIGS may help reduce the burdens of patients' compliance with medication schedules and side effects associated with medical therapy (17). Suboptimal compliance to medical therapy to manage glaucoma is common and has been linked to poor outcomes and increased health care costs.

Femtosecond lasers for ophthalmic surgery have been commercially available since 1999 (18; 19; 20). The ViaLase Laser is a femtosecond laser that is similar to other femtosecond surgical lasers, specifically, it is an infrared femtosecond laser that creates incisions in tissue using an imaging system with a livevideo camera that monitors the surgical area (20; 21). The mechanism of operation and the safety profile of the ViaLase Laser is the same as other marketed femtosecond laser devices used in LASIK and cataract surgery. Unlike previous devices, the ViaLase Laser incorporates a specialized optical delivery system that directs the surgical laser and imaging light through the peripheral cornea, into the iridocorneal angle, and onto the surgical area over the trabecular meshwork (Figure 1).

The ViaLase Laser is intended to create trabecular canals or apertures to increase the flow of aqueous humor through the trabecular meshwork, juxtacanalicular tissue, and inner wall of Schlemm's canal for the treatment of open angle glaucoma.

[figure not shown]

Figure 1 – Illustration showing the general optical path of the surgical beam to the iridocorneal angle.

1.3 Study Objective

To obtain initial evidence of safety of image guided, femtosecond laser glaucoma surgery using the ViaLase Laser for the treatment of primary open angle glaucoma. The ViaLase Laser is intended to create apertures through the trabecular meshwork for drainage of aqueous humor in the treatment of open angle glaucoma.

1.4 Study Design

This is a prospective, single-center, and single arm clinical trial of ViaLase Laser for the treatment of open angle glaucoma. Subjects will be screened for qualification as per the inclusion/exclusion criteria and must meet the inclusion/exclusion criteria in at least one eye to be enrolled. Up to 20 subjects will be consented as per the informed consent process. Subjects will be treated with the ViaLase Laser in one eye and followed for 12 months.

Eligible subjects will be examined preoperatively to obtain ocular and medical history and to establish a baseline ocular condition. Baseline and postoperative measurements will include distance visual acuity (best corrected), manifest refraction, intraocular pressure (IOP at baseline, 6 months and 12 months required), slit-lamp examination, gonioscopy, visual field, dilated fundus examination, specular microscopy (at baseline, 6 months and 12 months), and pachymetry.

Subjects who are on IOP lowering medications will be allowed to continue prior to laser treatment and up to one-month post-treatment. It is the investigator's discretion whether to add, continue or stop the medications after one month.

1.5 Safety Outcomes

Safety outcomes are assessed immediately after laser surgery and over 12 months after surgery.

1.5.1 Immediate Safety Outcomes

Immediate safety outcomes will be assessed during the Operative day (day-0), 1-day and 1-week visits:

- Percentage patients with elevated IOP equal or greater than 6 mmHg at 1-hour post-treatment
- Percentage of patients with iritis, anterior chamber flare and cells
- Percentage of patients with hyphema
- Percentage of patients with corneal haze

Percentage of patients with hypotony

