3.3 Preoperative Evaluation

Preoperative evaluation consists of two patient visits, a screening visit, and a baseline visit. During the screening visit, occurring 1 to 30 days prior to the baseline visit, the investigator informs the subject of the study and, after the subject provides consent, the investigator collects initial subject data including the subjects, demographics, ocular history, a list of ocular and non-ocular medications, and medical history. The investigator will also assess the subjects corrected visual acuity and perform a slit lamp examination.

During the baseline visit, occurring 3 to 60 days prior to the operative day, the investigator confirms the subject's list of ocular and non-ocular medications. The investigator then performs manifest refraction, best corrected spectacled visual acuity, and an endothelial cell count.

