3.4.2 Operative

• Surgery – Visit 3 (Day 0 occurring ≥ 3 days and ≤ 60 days after Baseline)

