3.5 Schedule of Visits and Clinical Assessments

All required clinical assessments should be performed at each scheduled visit as specified in Appendix A. Methods for performing assessments are described in Appendix B.

For interim visits, clinical assessments that are required by the protocol or as deemed necessary by the Investigator will be conducted. Assessments will be performed according to methods described in Appendix B and recorded on an interim visit CRF. Unscheduled visit clinical assessments will be conducted according to standard of care and documented on an unscheduled visit CRF.

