3.9 Statistical Methods

Descriptive statistics will be used for reporting available study results. Baseline and demographic characteristics will be presented. Continuous variables will be summarized by descriptive statistics such as mean, standard deviation, median, minimum, and maximum. Discrete variables will be summarized by frequency tables and percentages.

Adverse events will be summarized by presenting the number and percentage of patients experiencing any adverse event. Any other information collected such as seriousness, severity, and relationship to study device and procedure will be listed as appropriate.

IOP change from baseline will be summarized at each evaluation by mean, standard deviation, and range. Changes in IOP from baseline (Day 0 prior to assigned treatment) will be summarized at each visit. The proportion of subjects with an IOP reduction of 20% or more from baseline will be tallied at each post-operative visit. The number and frequency of medications will be tallied at each visit.

Slit lamp exam and fundus exam findings will be summarized at each visit using frequency and percentage.

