APPENDIX A – SCHEDULE OF VISITS AND CLINICAL ASSESSMENTS

Table B – Table of Scheduled Visits and Clinical Assessments

Visit Windows	Screening	Baseline	Operative Day 0	Day 1	Week 1	Month 1	Month 3	Month 6	Month 12
Window Range	1-30 days before Baseline	3-60 days before Operative	3-60 days after Baseline	1-day post-op	5-9 days post-op	21-35 days post-op	70-105 days post-op	168-196 days post-op	330-420 days post-op
Informed Consent	Х								
Demographics	Х								
Ocular History	Х								
Ocular Medication Assessment	Х	Х		Х	Х	Х	Х	Х	Х
Medical History	Х								
Medication Assessment	Х	Х		Х	Х	Х	Х	Х	Х
Pinhole VA (Snellen)				Х	Х				
Corrected VA (CVA)	X ¹			Х	Х	X ²	X ²	X ²	Х
Manifest Refraction		Х							Х
Best Spectacle Corrected VA (ETDRS)		Х							Х
Endothelial Cell Density		X				Х		Х	X
Slit Lamp Exam ³	Х			X	X	X	X	Х	X

 $^{^{\}rm 1}$ Snellen chart will be used for assessing corrected VA at the Screening visit.

² ETDRS chart will be used for assessing corrected VA at Months 1, 3 and 6. If corrected VA indicates a greater than or equal to 10 letter loss from screening, a refraction should be performed followed by a best spectacle corrected VA assessment using an ETDRS chart.

³ Slit lamp exam includes lenticular opacity grading.

Visit Windows	Screening	Baseline	Operative Day 0	Day 1	Week 1	Month 1	Month 3	Month 6	Month 12
Window Range	1-30 days before Baseline	3-60 days before Operative	3-60 days after Baseline	1-day post-op	5-9 days post-op	21-35 days post-op	70-105 days post-op	168-196 days post-op	330-420 days post-op
IOP via Goldmann Applanation Tonometry	Х		X ⁴	Х	X	Х	Х	Х	
Diurnal IOP via Goldmann Applanation Tonometry (8:00 am, 12:00pm, and 4:00 pm)		Х					Х		Х
Gonioscopy	Х				X	X	X	X	X
Dilated Fundus Exam ⁵	Х					Х	Х	Х	Х
Visual Field ⁶		Х					Х	Х	
Pachymetry	Х							Х	Х
Ocular Biometry	Х								
Surgery			Х						
Adverse Event Assessment	Х	Х	Х	Х	Х	Х	Х	Х	
Exit									Х

⁴ IOP will be assessed after surgery on Day 0 and can be done at any time per investigator discretion

⁵ Includes vertical C/D ratio assessment.

⁶ Subjects with a visual acuity at screening of 20/100 or worst are not required to have a visual field performed.

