- 4. Nuclear opacity
 - a. Orient beam at 45° to viewing axis.
 - b. Adjust slit beam to standard parameters: 8 mm height and 0.3 mm width.
 - c. Compare opalescence of nucleus with that in standard photos.
- 5. Cortical and PSC opacities
 - a. Select wide slit beam setting optimum for retro-illumination of lens.
 - b. Visualize lens opacities against red fundus reflex background Count only opacities visible against red reflex.
 - c. Mentally combine all cortical opacities into contiguous area.
 - d. Compare total opacity area with that in standard photos.
- 6. Classify each opacity with scale defined by 3 standard photos.
- 7. Select nearest half-step.

- a. Similar to standard or between two standards.
- b. Obviously less than mildest standard or greater than most.

[figure not shown]

Figure 3 – AREDS 2008 Lens Opacity Standard

B.5 Applanation Tonometry

Applanation tonometry using a Goldmann tonometer will be used to measure intraocular pressure (IOP) at all visits. At each visit, IOP will be measured prior to gonioscopy or dilation of the pupil. Subjects should be instructed to take their medication(s), if any, as usual the day of the visit.

IOP will be measured by 2 observers. Observer 1 (masked to real time IOP reading) will look through the slit lamp and turn the dial, with Observer 2 using the sponsor supplied IOP dial view blocking card and associated procedure. Observer 2 will read the result from the Goldmann tonographer knob and record the IOP readings.

At each IOP timepoint measurement, two measurements will be taken, and the mean recorded on the case report form unless they differ by more than 2 mmHg, in which case a third measurement is taken and the mean is computed.

Tonometer calibration for all study tonometers used in the study must be performed monthly and documented in the calibration log in the study regulatory binder.

B.6 Gonioscopy

Gonioscopy will be performed on all subjects and will be used to assess angle abnormalities including presence of goniosynechiae, angle anatomy and stent location (post-implantation). Please refer to Appendix A. At the screening exam, the Shaffer system for grading the angle anatomy will be used as follows:

B.6.1 Gonioscopic Angle Grade

Tuble E domoscope Angle drude Scheme					
Angle - θ	Grade				
0° ≤ θ < 10°	Closed				
10° ≤ θ < 15°	1				
15° ≤ θ < 25°	II				
25° ≤ θ < 35°	III				
> 35°	IV				

Table E – Gonioscope Angle Grade Scheme

B.7 Visual Field Examination

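### The schedule permits but does not assure the reading that the 1-hour IOP-elevation safety outcome needs, and the outcome does not say what the rise is measured from

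*Combined protocol and SAP*

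**What the plan says.** Section 1.5.1 lists as its first immediate safety outcome: "Percentage patients with elevated IOP equal or greater than 6 mmHg at 1-hour post-treatment". The synopsis (Section 1.1.3) has the same wording.

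Section 3.5 states: "All required clinical assessments should be performed at each scheduled visit as specified in Appendix A". In Appendix A the Operative Day 0 column carries one IOP mark, and its footnote 4 reads: "IOP will be assessed after surgery on Day 0 and can be done at any time per investigator discretion".

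On the reference value, Section 3.9 says: "Changes in IOP from baseline (Day 0 prior to assigned treatment) will be summarized at each visit". The visit called Baseline falls on another day. The Preoperative Evaluation section places it as follows: "During the baseline visit, occurring 3 to 60 days prior to the operative day". Section 3.4.2 agrees: "Day 0 occurring ≥ 3 days and ≤ 60 days after Baseline". Section B.5 of Appendix B adds: "Applanation tonometry using a Goldmann tonometer will be used to measure intraocular pressure (IOP) at all visits". It gives no clock time relative to the laser.

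**The concern.** The percentage needs two things from each treated eye: a reading at 1 hour, and a reference from which a rise of 6 mmHg is counted. The visible text secures neither. The outcome fixes the time, but the schedule leaves it open. The outcome says elevated without saying over what, whereas the adverse-event criterion in Section 3.7.2 (a rise of 10 mmHg or more) does name baseline.

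The stated objective is initial evidence of safety. If Day 0 readings are taken at differing times, or compared with differing references, the reported percentage no longer measures what its label says, and a reader of the report could not tell. The analysis is descriptive, with no test and no success threshold. What is at stake is therefore whether the figure can be computed and interpreted, not an error rate.

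**Working it through.** The plan gives no figure of its own for this outcome, so there is none to reproduce. The check is mainly a comparison of texts.

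**1. Timing.**
- Outcome (Sections 1.1.3 and 1.5.1): 1 hour after treatment.
- Schedule (Appendix A, made binding by Section 3.5): one Day 0 IOP reading, after surgery, at a time the investigator chooses.
- Method (B.5): IOP at every visit, with no time relative to the laser.
- Visible Postoperative Instructions: no reading time.

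A reading at 1 hour satisfies all four. A reading at any other time that day satisfies the last three and leaves the outcome without its value. The schedule therefore permits a 1-hour value but does not assure one.

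**2. Could 6 mmHg be an absolute level?** Inclusion criterion 5 (Section 1.7.1) requires a mean screening IOP on medication of 21 to 35 mmHg. To avoid counting as an event under an absolute reading, an eye still at its screening value would have to fall below 6 mmHg:
- from 21 mmHg: a fall of more than 21 − 6 = 15 mmHg, or 15/21 = 71%;
- from 35 mmHg: a fall of more than 35 − 6 = 29 mmHg, or 29/35 = 83%.

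Nearly every eye would count, and Section 3.7.2 uses IOP below 6 mmHg for hypotony. The outcome must mean a rise.

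**3. A rise from what?**
- Section 3.9's baseline, Day 0 before treatment. This is the natural choice, but Appendix A marks no such reading: footnote 4 places the one Day 0 mark after surgery.
- The Baseline visit, 3 to 60 days before surgery, with three diurnal readings. It is scheduled, but it is not Section 3.9's baseline.

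The reference that the statistical section names has no visible mark, and the scheduled one is not the one named.

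**4. Size.** Let n be the number of treated eyes (one per subject), k the number without a valid 1-hour comparison, and x the rises seen among the rest. Over all treated eyes the percentage lies between x/n and (x + k)/n, a width of k/n. Consent is capped at 20 subjects, so n is at most 20 and each such eye costs at least 1/20 = 5 points. The documents do not give k. Assuming n = 20:

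| k (assumed) | width k/20 |
|---|---|
| 1 | 5 points |
| 2 | 10 points |
| 5 | 25 points |

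For example, with k = 5 and x = 2, the percentage among eyes with a reading is 2/15 = 13.3%, while the bounds over all eyes are 2/20 = 10% and 7/20 = 35%.

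**The case against.** The strongest objection is redaction. The text between Preoperative Care and Postoperative Instructions has been removed, and a pre-laser check and a 1-hour check could well be written there. This stands as a limit: a reader might infer that the trial never planned these readings, and the documents do not support that. It does not remove the point, because footnote 4 and the outcome wording are both visible. If the hidden text requires a 1-hour reading, the footnote's open timing conflicts with it; if it does not, the outcome has no assured data.

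Second, footnote 4 and the outcome do not strictly contradict each other, since an investigator can satisfy both by measuring at 1 hour. This is correct, and it is why the claim is only that the value is not assured.

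Third, a reader might take Section 1.4's parenthesis, "IOP at baseline, 6 months and 12 months required", as confirmation that no 1-hour reading is required. It cannot bear that weight. It also leaves out Day 1, Week 1, Month 1 and Month 3, all of which Appendix A marks for IOP, so it is not a full list.

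Fourth, Section 3.9 largely supplies the reference, and its unmarked reading affects every IOP-change summary, not this outcome alone. Both statements are fair. The outcome still does not cite that baseline, and the visible schedule still does not collect it.

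Finally, a reader might infer that rises of 6 to under 10 mmHg would go unrecorded. They need not. Section 3.9 summarises IOP change with its range at each evaluation, clinically significant changes are adverse events, and a paracentesis for a pressure rise goes on the case report form. None of these yields the stated percentage.

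**Conclusion.** The point holds in a limited form and should be fixed. The visible outcome, schedule and statistical section do not agree on when the Day 0 IOP is read or what it is compared with. A site could comply with Appendix A and leave the first-listed immediate safety outcome without its value.

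The loss is at least 5 percentage points of indeterminacy per affected eye. That figure rests only on the ceiling of 20 subjects; the counts of 1, 2 and 5 eyes are illustrations. No rate of falsely counted rises is claimed for an earlier-day reference, because the documents give no between-day variability. Confidence is medium, since the redacted operative text could settle what is actually measured, though not the wording of the footnote or the outcome.

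**What to change.** Reconcile Sections 1.1.3, 1.5.1 and 3.9 with Appendix A.

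1. Amend footnote 4 so that the Day 0 post-surgery reading is taken at the protocol's own 1-hour point, within a window the sponsor states. Any further readings stay discretionary.
2. Word the outcome as an increase of at least 6 mmHg over the Section 3.9 baseline, and mark that pre-laser Day 0 reading in Appendix A. If the sponsor means the Baseline visit instead, amend Section 3.9 to match and say which of its readings is used.
3. Report the number of treated eyes with and without an in-window reading. Give the percentage among eyes with a reading, together with the lowest and highest values possible over all treated eyes. A denominator of in-window eyes alone could mislead.

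Cost: a fixed time for a reading already planned and, unless the redacted text already requires it, one added pre-laser tonometry timepoint. Under B.5 that means two observers and two or three measurements. No treatment rule changes. If the redacted text already requires both readings, only the footnote, the table mark, the outcome wording and the reporting line need editing.
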